7.1 Study Objectives

The primary objectives of the study are to assess the safety, tolerability and immunogenicity of the study vaccine.

7.1.1 Safety (all 3 age groups)

All unsolicited AEs and SAEs reported after participants are exposed to the study product and up to 28 days post last study injection are included in the primary analysis of safety.

To assess safety, the number and percentage of participants experiencing at least one AE, and the number and percentage of participants experiencing each specific AE, categorized by body system and preferred term, is tabulated by study cohort and product received along with their corresponding exact binomial (Clopper-Pearson) 95% confidence intervals. Overall summaries by cohort and by product received include the number and percentage of participants experiencing: (1) any SAE; (2) any adverse experience; (3) any Grade 2 or greater AE; (4) any AE judged related to study product; (5) any Grade 2 or greater AE judged related to study product (**Table 14.3.2.1**). In addition, AEs will be summarized by grade. P-values from statistical analyses will be reported only for the primary endpoints listed in section 4.1.1.

7.1.2 Tolerability

All local reactions and systemic reactogenicity reported up to 7 days post vaccination are included. To assess tolerability, the number and percentage of participants with Grade 2 or higher local or systemic reactions is tabulated by study cohort and by product received along with their corresponding 95% confidence intervals. Local and systemic reactions are tabulated separately. Overall summaries by cohort and by product received will include the number and percentage of participants experiencing: (1) each specific reaction at Grade 2 or greater after each injection; (2) each specific reaction at Grade 2 or greater after any injection; (3) any reaction at Grade 2 or greater after each injection; and (4) any reaction at Grade 2 or greater after any injection (**Table 14.3.1.1 for local** and **Table 14.3.1.2 for systemic**). Descriptive statistics will be used to summarize the duration of local and systemic reactions. In addition, local and systemic reactions will be summarized by grade.

7.1.3 Clinical laboratory values

Changes in clinical laboratory values between baseline and one week after vaccination will be analyzed descriptively.

Anti-P2-VP8 Fold-Rise (FR) from Pre-Vaccination will be presented by treatment and time-point. This analysis will be separately presented for adults, toddlers and infants; IgG & IgA seroresponses; and three vaccine antigens (P[2], P[4], P[6]). An ANOVA or Kruskal-Wallis test will be conducted to assess the difference between treatment groups in mean log (base10) FR. Separate p-values will be presented at each time-point. Two-sided 95% CI for the geometric mean fold rise for each treatment group will be obtained using a t-distribution on log transformed fold rise measurements. For infants, analysis of IgG will be conducted two ways 1) Unadjusted for Maternal Antibodies 2) Adjusted for Maternal Antibodies.

Number and Proportion of subjects with Anti-P2-VP8 seroresponse (at least a 4-fold rise in anti P2-VP8 titer from baseline) will be presented by treatment and time-point. This analysis will be separately presented for adults, toddlers and infants; IgG & IgA seroresponses; the three vaccine antigens (P[2], P[4], P[6]); subjects with seroresponses to all 3 vaccine antigens and to each of the 3 specific pairs of vaccine antigens. The proportion of participants with a positive response at a specific time point will be evaluated using the 2-sided exact binomial (Clopper-Pearson) 95% CI for each treatment group. A logistic regression analysis will be performed to test the overall treatment effect. Separate p-values will be presented at each time-point. For infants, analysis of IgG will be conducted two ways 1) Unadjusted for Maternal Antibodies 2) Adjusted for Maternal Antibodies.

Analysis of Neutralizing Antibody Responses

Descriptive statistics and analysis of neutralizing antibody titers will be presented by treatment and time-point. This analysis will be separately presented for adults, toddlers and infants and each rotavirus strain (Wa, DS-1 and 1076) as well as heterologous strains. An ANOVA or Kruskal-Wallis test will be conducted to assess the difference between treatment groups in mean log (base10) titer. Separate p-values will be presented at each time-point. Two-sided 95% CI for the geometric mean titer (GMT) for each treatment group will be obtained using a t-distribution on log transformed titers/levels.

Neutralizing antibody Fold-Rise (FR) from Pre-Vaccination will be presented by treatment and time-point. This analysis will be separately presented for adults, toddlers and infants and each rotavirus strain (Wa, DS-1 and 1076) as well as heterologous strains. An ANOVA or Kruskal-Wallis test will be conducted to assess the difference between treatment groups in mean log (base10) FR. Separate p-values will be presented at each time-point. Two-sided 95% CI for the geometric mean fold rise for each treatment group will be obtained using a t-distribution on log transformed fold rise measurements. For infants, analysis will be conducted two ways 1) Unadjusted for Maternal Antibodies 2) Adjusted for Maternal Antibodies.

Number and Proportion of subjects with neutralizing antibody response (at least a 2.7-fold and a 4-fold rise in neutralizing antibody titers from baseline) will be presented by treatment and time-point. This analysis will be separately presented for adults, toddlers and infants; and each of the three rotavirus strains (Wa, DS1, 1076) as well as heterologous strains. The proportion of participants with a positive response at a specific time point will be evaluated using the 2-sided exact binomial (Clopper-Pearson) 95% CI for each treatment group. A logistic regression analysis will be performed to test the overall treatment effect. Separate p-values will be presented at each time-point. For infants, analysis will be conducted two ways 1) Unadjusted for Maternal Antibodies 2) Adjusted for Maternal Antibodies.

Number and Proportion of subjects with a neutralizing antibody response against at least **2 of the 3** rotavirus strains (Wa, DS1, 1076), against all 3 rotavirus strains and against each of the 3 specific pairs of rotavirus strains will be presented by treatment group and time-point. The proportion of participants with a positive response at a specific time point will be evaluated using the 2-sided exact binomial (Clopper-Pearson) 95% CI for each treatment group. A logistic regression analysis will be performed to test the overall treatment effect. Separate p-values, estimates and 95% confidence intervals from the logistic regression will be presented at each time-point. For infants, analysis will be conducted two ways 1) Unadjusted for Maternal Antibodies 2) Adjusted for Maternal Antibodies.

Analysis of Anti-rotavirus IgA Responses to Whole Viral Lysate

Descriptive statistics and analysis of anti-rotavirus to whole lysate will be presented by treatment and time-point for infants only. An ANOVA or Kruskal-Wallis test will be conducted to assess the difference between treatment groups in mean log (base10) response. Separate p-values will be presented at each time-point. Two-sided 95% CI for the geometric mean titer (GMT) for each treatment group will be obtained using a t-distribution on log transformed titers/levels.

Fold-Rise (FR) from Pre-Vaccination in anti-rotavirus to whole lysate will be presented by treatment at 4 weeks post final vaccination. An ANOVA or Kruskal-Wallis test will be conducted to assess the difference between treatment groups in mean log (base10) FR. Two-sided 95% CI for the geometric mean fold rise for each treatment group will be obtained using a t-distribution on log transformed fold rise measurements.

Number and Proportion of subjects with an anti-rotavirus to whole lysate response (at least a 4-fold rise from baseline) will be presented by treatment at 4 weeks post final vaccination. The proportion of participants with a positive response will be evaluated using the 2-sided exact binomial (Clopper-Pearson) 95% CI for each treatment group. A logistic regression analysis will be performed to test the overall treatment effect.

7.1.5 Rotarix Shedding

Assessment of shedding of Rotarix virus is performed for each of the three specified post-vaccination days (Days 89, 91 and 93, i.e., 5, 7 and 9 days after the first Rotarix administration) and for shedding on any of the three days. The primary of these analyses will be for shedding on any of the three days. Additionally, the effect of IgA, IgG and Nab responses (2.7-fold and 4-fold rise on day 84) on shedding of Rotarix virus (at any time) will be analyzed, by each of the 3 antigens (for IgA and IgG) and 3 rotavirus strains (NAb). The proportion of participants with shedding at a specific time point and at any time point will be evaluated using the 2-sided exact binomial (Clopper-Pearson) 95% CI for each treatment group. A logistic regression analysis will be performed to test the overall treatment effect and separate p-values will be presented for each time-point and overall.

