2.3.4 Definitions and Derivations

The following definitions and derivations will be used in this study:

- Diarrhea is defined as ≥ 3 looser than normal stools in a 24 hour period.
- A baseline value will be defined as the last value obtained prior to the first vaccination of study product.
- Age will be calculated from the date of enrollment and will be presented in whole years for adults, months for toddlers and days for infants (truncated integer).
- The calculations for GMTs will be performed by taking the anti-log of the arithmetic mean of the \log_{10} -transformed titers.
- Fold increase/rise from baseline will be calculated as the following:

$$\text{Ratio of: } \frac{\text{post-immunization titer}}{\text{pre-immunization titer}}$$

- Calculation of geometric mean fold rise (GMFR) will be performed by taking the anti-log of the arithmetic mean of the difference in \log_{10} titers, where

$$\text{Difference} = (\text{post-immunization } \log_{10} \text{titer}) - (\text{pre-immunization } \log_{10} \text{titer})$$

- Antibody responses are defined as:
 - **Anti-P2-VP8 IgG & IgA seroresponses by ELISA:** 4-fold increase from baseline in antibody titers in assays using each of the three vaccine antigens (P[4], P[6] and P[8]).
 - **Neutralizing antibody responses:** 2.7-fold increase from baseline in antibody titers to each of the three rotavirus strains from which the vaccine antigens are derived, as well as heterologous strains.
- Prior medications are those medications that started and stopped prior to study vaccination.

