3.4.2 Immunogenicity Variables

Antibody (IgG and IgA by ELISA) to P2-VP8 and Rotavirus neutralization analyses will be performed on sera from the following visits:

		4 Weeks Post Vac.1 Day 28	4 Weeks Post Vac.2 Day 56	4 Weeks Post Vac.3 Day 84
	Screening			
Adults:	X	X	X	X
Toddlers:	X	X		
Infants:	X		X	X

Anti-rotavirus IgA (whole viral lysate) by ELISA will be determined in serum samples collected at baseline and one month after the final study injection (i.e., day 84).

Additional immunogenicity assays may be performed by research laboratories to further evaluate post-study injection immune responses and to explore whether correlates of protection may be identified

For immunogenicity variables, data inferior to the Lower Limit of Quantification (LLOQ) will be replaced by half the detection limit; data superior to the Upper Limit of Quantification (ULOQ) will be replaced by the limit (truncated data). No search for outliers will be performed. Prior to statistical analysis, all immunology data will be \log_{10} transformed to improve the distributional properties of the data and reduce the impact of potential outliers.

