4 SAMPLE SIZE CONSIDERATIONS

4.1.1 Primary Safety Endpoints

Safety will be assessed by analyses of the following primary endpoints (events), where the unit of analysis in each case will be the proportion of participants with at least one event:

- Moderate or greater solicited local reactions
- Moderate or greater solicited systemic reactions
- Moderate or greater adverse events
- Moderate or greater adverse events where there is a reasonable possibility that the study product caused the event, i.e., are suspected adverse reactions
- Serious adverse events

It was assumed that almost all participants enrolled would provide data for safety analysis and at least 90% of enrolled participants would be evaluable for immunogenicity assessments.

Safety

The sample size for this study was selected to detect frequent adverse events. Given a planned sample size of 12 vaccine recipients per dose group and 24 vaccine recipients for the two dose groups combined in both adults and toddlers (A and B), the study will have an approximately 90% chance of observing at least one AE that occurs at a rate of 17.5% and 9.2%, respectively. For the two infant cohorts combined (C and D), 150 vaccine recipients per dose group and 450 vaccine recipients for the three dose groups combined will provide at least 90% chance of observing an AE that has a 1.6% and 0.5% rate of occurrence, respectively.

Conversely, if no SAEs are observed in 24 and 450 vaccine recipients, the study will be able to rule out SAEs occurring at a rate of approximately 11.7% and 0.7%, respectively based on the upper bounds of the one-sided 95% confidence.

Primary Immunogenicity Endpoints

Based on the results in South African infants who received monovalent P2-VP8 vaccine or placebo (VAC-013), the strain specific seroresponse rates for both P2-VP8 vaccine doses were expected to be $\geq 80\%$ for at least one of the three P2-VP8 vaccine doses and $<20\%$ for the placebo group. For the two infant cohorts combined, with 135 evaluable recipients per dose level (assuming 10% loss), this study was designed to provide at least 74% and 95% power (Fisher's exact 2-tailed test) to detect 15 and 20 percentage points

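### The antibody–shedding analysis in SAP 7.1.5 uses only yes/no 2.7-fold and 4-fold responses; a continuous log10 fold-rise model should be added beside them

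*SAP*

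**What the plan says.** Section 7.1.5 makes shedding on any of the three stool days the main shedding outcome. It then adds an analysis of antibody against that outcome: "the effect of IgA, IgG and Nab responses (2.7-fold and 4-fold rise on day 84) on shedding of Rotarix virus (at any time) will be" done separately for the three antigens (IgA, IgG) and the three strains (neutralizing antibody). It names no titer or fold-rise on a continuous scale as a predictor, and no other section relates antibody to shedding.

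Section 2.3.4 defines the responses as threshold crossings: for ELISA, "4-fold increase from baseline in antibody titers in assays using each of the three vaccine antigens"; for neutralization, "2.7-fold increase from baseline in antibody titers to each of the three rotavirus strains". Section 7.1.4 also tabulates a 4-fold neutralizing response.

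Elsewhere the measurements are kept continuous. Section 3.4.2 says that "all immunology data will be \log_{10} transformed to improve the distributional properties of the data", and section 7.1.4 compares mean log10 titer and mean log10 fold-rise between treatment groups.

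On expected response, section 4.1.1 says that strain-specific rates "were expected to be $\geq 80\%$ for at least one of the three P2-VP8 vaccine doses and $<20\%$ for the placebo group".

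**The concern.** Reducing a continuous predictor to yes or no discards the differences on each side of the cut. A 4-fold and a 100-fold riser count the same. Where most vaccinees respond, few non-responders are left to compare them with. With low placebo response, a split across all arms also partly repeats vaccine versus placebo.

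The SAP gives no reason for leaving the log10 scale here, and the data for a continuous model will already exist. The stool subset comes from one site (section 3.2) and its size is not stated, so lost information is hard to make up. At stake is the reading of a null result: a graded relation between antibody and shedding could be missed and reported as no relation.

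**Working it through.** **Inputs from the SAP.** Response thresholds (2.3.4, 7.1.5); expected response of at least 80% in at least one dose and below 20% on placebo (4.1.1); vaccine to placebo 3:1 in infants (Group C 36:12, Group D 414:138; 3.2); two-sided 0.05 (section 7).

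**The plan's own figures.** The SAP states no power for the antibody–shedding analysis, so there is nothing to reproduce directly. Its neighbouring infant figures, at 135 per group, do reproduce to within about one point: Fisher's exact test gives 75.3% for 65% vs 80% (stated 74%) and 93.9% for 60% vs 80% (stated 95%). For a 2-fold GMT difference with SD 0.6, 0.301 / (0.6 × √(2/135)) = 4.12, giving 98.4% (stated 98%).

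**Step 1: within an arm.** If log fold-rise is normal and a share p exceeds the cut, the information kept relative to the continuous measure is φ(z)² / (p(1 − p)), where z is the normal quantile of p. This is the squared correlation between the cut and continuous versions, and the relative efficiency for a weak log-linear effect.

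- At p = 0.80: z = 0.842, φ(z) = 0.280, so 0.0784 / 0.16 = 0.49.
- At p = 0.50: 0.3989² / 0.25 = 0.64.

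| Responding | Kept | Lost |
|---|---|---|
| 50% | 64% | 36% |
| 60% | 62% | 38% |
| 75% | 54% | 46% |
| 80% | 49% | 51% |
| 90% | 34% | 66% |

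The loss reaches one half at 79.1% responding. The SAP does not state a 90% rate; that row only shows the direction.

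**Step 2: all arms pooled, unadjusted.** Take 3:1 allocation, unit SD within arm, and 80% and 20% responding. The arm means relative to the cut are then +0.842 and −0.842.

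- Overall responders: 0.75 × 0.80 + 0.25 × 0.20 = 0.65.
- Total variance: 1 + 0.1875 × 1.683² = 1.531.
- Covariance of measure and response: 0.743 − 0.421 × 0.65 = 0.469.
- Kept: 0.469² / (1.531 × 0.65 × 0.35) = 0.63.

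Over vaccine rates of 80–95% and placebo rates of 5–20%, the pooled cut keeps 63–72%, a loss of 28–37%. With arm in the model, the 80%/20% case returns to 49% kept.

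**Step 3: power, under assumptions.** The SAP gives no RMPRU share, shedding rate or effect size. I assume that one third of Group D is at RMPRU: 36 + 414/3 = 174 vaccinees, or 48 + 552/3 = 232 infants in all. I also assume an odds ratio of 1.6 per within-arm SD and 80% of vaccinees responding. Simulated logistic power:

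| Setting | Shedding | Continuous | Cut |
|---|---|---|---|
| 174 vaccinees | 20% | 68% | 43% |
| 174 vaccinees | 40% | 84% | 55% |
| 232 infants, pooled, 20% placebo response | 20% | 95% | 80% |
| 232 infants, pooled, 20% placebo response | 40% | 99% | 94% |

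For vaccinees only, across 100–250 infants, 20–40% shedding, odds ratios of 1.5–1.8 and 60–90% responding, the continuous model gains about 5 to 42 points.

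**Step 4: the opposite shape.** Suppose the true relation is a step exactly at the cut: 174 vaccinees, 80% responding, 30% shedding, odds ratio 3 across the step. Power is then about 53% for the continuous model and 78% for the cut, so the ranking reverses.

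**The case against.** The strongest reply is that the size depends on choices the SAP does not make. Section 7.1.5 neither restricts to vaccinees nor adjusts for arm, and placebo infants give stool samples too. In a pooled model the loss is about a third, and power can stay high. The 80% rate is expected "for at least one of the three P2-VP8 vaccine doses and" not for every dose or assay; the primary neutralizing hypothesis is 60% in at least one group. This stands, and it limits the claim. A reader might infer that the cut discards half or more of the information throughout; the SAP does not support that. The pooled analysis does, however, mix the antibody effect with the treatment effect.

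Second, the thresholds are the trial's own response definitions, and asking whether responders shed less is a coherent question. If protection works by threshold, the cut is the better analysis (step 4). This stands too. It is a reason to keep the responder analyses, not to omit a continuous one, since the SAP does not say which shape is expected.

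Third, a reader might take the mention of correlates of protection in section 3.4.2 as a goal that 7.1.5 fails to serve. That sentence concerns additional assays that research laboratories may perform, and sets no aim for the shedding analysis. A dose-level pattern also remains visible, because GMT, fold-rise and shedding are all reported by treatment group.

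**Conclusion.** The point holds as a gap in an exploratory analysis. Relying only on yes/no responses costs about 28–37% of the information with arms pooled, 36–46% within an arm where 50–75% respond, and about half where about 80% respond.

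These figures assume roughly normal log fold-rise within arm and a roughly log-linear effect. Values below the LLOQ are replaced and values above the ULOQ truncated (3.4.2), so normality is not assured. The power figures also rest on an assumed subset size, shedding rate and odds ratio.

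A reader might infer that the trial's conclusions are weakened. They are not: shedding is the single exploratory endpoint, its relation to antibody is an addition to that endpoint, and no primary or secondary conclusion depends on it.

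**What to change.** In section 7.1.5, add a logistic regression of any-day shedding on continuous log10 Day 84 fold-rise, separately for each antigen (IgG, IgA) and strain (neutralizing antibody).

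- Include treatment arm in the model, and show the unadjusted version alongside.
- Report the odds ratio per 2-fold or 10-fold higher fold-rise with its 95% CI.
- Check linearity, for example with a quadratic term or tertiles.
- Give log10 Day 84 titer as a sensitivity predictor only, because in infants it includes residual maternal antibody.
- Keep the 2.7-fold and 4-fold responder analyses.

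The cost is SAP wording and a few extra models on data already collected, with no new samples or participants. The downside is the log-linearity assumption and more results to report from an exploratory subset.

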2.1.3 Exploratory Objectives

Efficacy

- To evaluate the impact of the trivalent P2-VP8 subunit rotavirus vaccination on shedding of Rotarix subsequently administered in healthy South African infants as a test of concept.

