3.2 STUDY SCHEMA

Group		Trivalent P2-VP8 Dose	N	-7 ^a to -1	0	7	28	56	84	89, 91, 93	168	224
A Adult	A1	30 µg	12	B(S,I)	X	B(S)	X, B(I)	X, B(I)	B(I)			F
		Placebo	3	B(S,I)	P	B(S)	P, B(I)	P, B(I)	B(I)			F
	A2	90 µg	12	B(S,I)	X	B(S)	X, B(I)	X, B(I)	B(I)			F
		Placebo	3	B(S,I)	P	B(S)	P, B(I)	P, B(I)	B(I)			F
A Total			30									
B Toddler	B1	30 µg	12	B(S,I)	X	B(S)	B(I)				F	
		Placebo	3	B(S,I)	P	B(S)	B(I)				F	
	B2	90 µg	12	B(S,I)	X	B(S)	B(I)				F	
		Placebo	3	B(S,I)	P	B(S)	B(I)				F	
B Total			30									
C Infant	C1	15 µg	12	B(S,I)	X	B(S)	X	X, B(I)	B(I)	Sh		F
		Placebo	4	B(S,I)	P	B(S)	P	P, B(I)	B(I)	Sh		F
	C2	30 µg	12	B(S,I)	X	B(S)	X	X, B(I)	B(I)	Sh		F
		Placebo	4	B(S,I)	P	B(S)	P	P, B(I)	B(I)	Sh		F
	C3	90 µg	12	B(S,I)	X	B(S)	X	X, B(I)	B(I)	Sh		F
		Placebo	4	B(S,I)	P	B(S)	P	P, B(I)	B(I)	Sh		F
C Total			48									
D Infant		15 µg	138	B(S,I)	X		X	X, B(I)	B(I)	Sh		F
		30 µg	138	B(S,I)	X		X	X, B(I)	B(I)	Sh		F
		90 µg	138	B(S,I)	X		X	X, B(I)	B(I)	Sh		F
		Placebo	138	B(S,I)	P		P	P, B(I)	B(I)	Sh		F
D Total			552									
All Cohorts Total			660									

X = Trivalent P2-VP8 vaccine

P = placebo

B = blood sample for (S) safety and/or (I) immunogenicity testing

F = final study f/u visit/call

Sh = stool samples to assess Rotarix shedding. Only at RMPRU (Soweto).

^aFor adult and toddler cohorts, -28 to -1

For each age group, progression from one dose level to the next will require review of clinical and safety lab data through 7 days after the first dose at the lower dose level. Safety laboratory blood specimens will be drawn at baseline for all participants (screening) and 7 days after first study injection in Groups A, B and C.

[figure not shown]
Blood samples for immunogenicity analysis will be obtained at baseline for all participants, Days 28, 56 and 84 for Group A (adults), Day 28 for Group B (toddlers), and Days 56 and 84 for Groups C and D (infants).

Stool samples to assess Rotarix shedding will be obtained from infants (Groups C and D) on days 89, 91 and 93 (i.e., 5, 7 and 9 days after the first Rotarix dose on day 84) in the subset of infants enrolled at the Respiratory and Meningeal Pathogens Research Unit (RMPRU).

For each dose level, progression from adults in Group A to toddlers in Group B and then to infants in Group C will require review of clinical and safety laboratory data through 7 days after study injection in the older group. (see Figure 1)

These determinations will be made by the Safety Review Committee (SRC).

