5.8 Multiple Comparisons/Multiplicity

For each event/endpoint, a multiplicity adjustment for 4 treatment groups will be applied using a sequential testing approach by performing an overall comparison of all treatment groups prior to pairwise comparisons. No multiplicity adjustment for multiple immunogenicity endpoints is planned, since the dose selection for the Phase 3 will be based on comprehensive statistical and clinical evaluation of all immunogenicity endpoints including safety results.

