7 STATISTICAL ANALYSIS

Descriptive statistics (mean, standard deviation, median, range) for continuous measures (e.g., age) and proportions for categorical measures (e.g., gender) will be summarized by treatment group. All percentages will be presented to one decimal place. Means, medians, standard deviations, confidence intervals, etc., will be presented as integers if the absolute value is greater than or equal to 100 in magnitude, to one decimal place if greater than or equal to 10, and 2 decimal places if less than 10. P-values will be reported to 4 decimal places.

For both safety and immunogenicity, when the use of descriptive statistics to assess group characteristics or differences is required, the following methods will be used: for categorical variables/responses, the number, proportion (% and exact 95% confidence interval) of participants in each category. For continuous variables/responses, the mean, median, standard deviation, quartiles and range, as well as the geometric mean and 95% confidence interval for immunogenicity outcomes. A non-parametric method (e.g., bootstrap or Wilcoxon rank sum test) will be used for continuous variables if the data are not consistent with the normal distribution.

The following methods will be used for formal testing of differences between study groups: for binomial response variables logistic regression will be used to test for an overall treatment effect and, if statistically significant, p-values from all pair-wise comparisons obtained from the regression model will be reported. Where multiple results are available for the same participant (e.g., reactogenicity after each vaccination), the correlation between results from the same participant will be taken into account by using a generalized mixed effects model, with treatment group as a fixed effect and participant as a random effect. For continuous variables that are not normally distributed, the overall treatment effect will be assessed by the Kruskal-Wallis test and if statistically significant, pair-wise comparisons will be performed using the Wilcoxon 2-sample test. For \log_{10} immunogenicity values the overall treatment effect will be assessed by ANOVA and if statistically significant, estimates of all pair-wise comparisons from the model will be reported.

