All testing and inference will be performed with a 2-sided p-value of 0.05. For each immunogenicity endpoint, a multiplicity adjustment for 4 treatment groups will be applied using a sequential testing approach by performing an overall comparison of all treatment groups prior to pair-wise comparisons. No multiplicity adjustment for multiple immunogenicity endpoints is planned, since the dose selection for the Phase 3 will be based on comprehensive statistical and clinical evaluation of all immunogenicity endpoints including safety results.

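### Rotarix shedding is compared between arms only through a four-arm overall test, so a non-significant result leaves no planned vaccine-versus-placebo estimate or interval

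*SAP*

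**What the plan says.** SAP Section 2.1.3 gives the exploratory, test-of-concept efficacy objective: "To evaluate the impact of the trivalent P2-VP8 subunit rotavirus vaccination on shedding of Rotarix subsequently administered in healthy South African infants". Section 7.1.5 selects the lead variable, "The primary of these analyses will be for shedding on any of the three days", and provides an exact interval for the proportion shedding in each arm. Its arm comparison is this sentence: "A logistic regression analysis will be performed to test the overall treatment effect and separate p-values will be presented for each time-point and overall".

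The general rules decide what follows that test. Section 7 says: "for binomial response variables logistic regression will be used to test for an overall treatment effect and, if statistically significant, p-values from all pair-wise comparisons". Section 5.8 applies the same order to every event and endpoint: "a multiplicity adjustment for 4 treatment groups will be applied using a sequential testing approach". The level is fixed by Section 7: "All testing and inference will be performed with a 2-sided p-value of 0.05".

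Stools are collected only "in the subset of infants enrolled at the Respiratory and Meningeal Pathogens Research Unit" (Section 3.2). Section 5.7 places all of Group C at that site and spreads Group D over three sites, without giving the split.

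**The concern.** The question is about vaccination, so the natural answer is a difference in shedding between vaccinated and placebo infants, with its uncertainty. The plan supplies a p-value for the hypothesis that four arms are equal. If that p-value exceeds 0.05, the rule stops there. The reader then has four separate proportions with intervals and no planned estimate of what the vaccine did. Even when the test is significant, Section 7 promises p-values for pairwise differences in binary outcomes, not effect sizes. The SAP does better elsewhere: for neutralizing responses to two of three strains, Section 7.1.4 promises estimates and 95% confidence intervals from the logistic model.

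This matters because shedding is the trial's only efficacy objective, and the study rationale treats it as a stand-in for efficacy. It is measured at one site, so numbers are limited. A contrast chosen after unblinding would carry less weight than one named now.

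**Working it through.** **Inputs from the SAP.** Group D is 552 infants randomized 1:1:1:1. Group C is 48 infants: 12 on each dose and 3 × 4 = 12 on placebo. The level is 0.05, two-sided. The SAP states no power, subset size or shedding rate for this endpoint, so it has no figure of its own to reproduce.

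**Assumptions.** If the stool site enrolled one third of Group D, the subset is 552/3 + 48 = 184 + 48 = 232 infants, or 58 per arm. Placebo shedding is taken as 50%. The dose patterns below are illustrative.

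**Method.** With n per arm and mean rate p̄, the noncentrality of the overall test is λ = n Σ(pᵢ − p̄)² / [p̄(1 − p̄)]. The pooled contrast uses the same formula with each dose rate replaced by the mean of the three. The trend over ordered arms, with equally spaced scores sᵢ = −1.5, −0.5, 0.5, 1.5, has λ = n (Σ sᵢpᵢ)² / [5 p̄(1 − p̄)].

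*Equal effects, 50/30/30/30%.* p̄ = 0.35 and Σ(pᵢ − p̄)² = 0.0225 + 3 × 0.0025 = 0.03. So λ = 58 × 0.03/0.2275 = 7.65 for both the overall and the pooled test. The pooled test spends it on 1 df and the overall test on 3 df.

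*Graded effects, 50/45/35/25%.* p̄ = 0.3875 and p̄(1 − p̄) = 0.2373.
- Overall: λ = 58 × 0.036875/0.2373 = 9.01.
- Pooled (50% against a mean of 35%): λ = 58 × 0.016875/0.2373 = 4.12. More than half of the signal lies between doses, and pooling discards it.
- Trend: Σ sᵢpᵢ = −0.425, so λ = 58 × 0.1806/(5 × 0.2373) = 8.83, nearly all of the signal on 1 df.

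**Simulated power** (40,000 trials per pattern, 58 per arm; likelihood-ratio tests for overall and pooled, Cochran-Armitage for trend):

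| Shedding, placebo/15/30/90 µg | 3-df overall | Pooled 1-df | Trend 1-df |
|---|---|---|---|
| 50/35/35/35% | 37% | 52% | 35% |
| 50/30/30/30% | 62% | 78% | 58% |
| 50/40/33/27% | 61% | 61% | 77% |
| 50/45/35/25% | 73% | 52% | 86% |
| 50/50/50/30% | 62% | 15% | 54% |

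- Equal effects: pooling gains 52 − 37 = 15 and 78 − 62 = 16 points.
- Graded effects: pooling gains 61 − 61 = 0 or loses 73 − 52 = 21 points. The trend gains 77 − 61 = 16 and, unrounded, 85.5 − 73.1 = 12.4 points.
- Top dose only: pooling loses 62 − 15 = 47 points, and the trend also trails the overall test.
- With no true effect, all three tests reject about 5% of the time.

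**Sensitivity under equal effects.** The 3-df test loses 10.3, 15.5, 16.9, 15.5, 11.6 and 7.9 points when pooled power is 30, 50, 70, 80, 90 and 95%. Over 48 to 600 infants, placebo shedding of 30 to 60% and relative risks of 0.5 to 0.7, the loss runs from 0 to 18 points. At 232 infants it runs from 4 to 18.

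**The case against.** The endpoint is exploratory, and the SAP uses one coherent rule for all binary endpoints: overall test first, then pairwise. The trial is also a dose comparison. Group D exists partly to compare the three doses, and Phase 3 dose selection is the stated reason for the multiplicity approach, so degrees of freedom spent between doses are not foreign to its purpose. The objective speaks of the impact of vaccination without specifying a pooled comparison. Per-arm proportions with exact intervals are reported whatever the overall test shows, so a shared reduction would be visible. Neither 1-df test beats the 3-df test everywhere: pooling fails under steep gradients, and the trend is slightly weaker when all doses act alike.

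All of this stands. It rules out calling the 3-df test an error or replacing it with the pooled contrast. It does not supply the missing comparison. Four separate intervals are not an estimate of the vaccine effect, and a test that serves dose comparison can sit beside one that answers the stated objective.

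**Conclusion.** Section 7.1.5 plans no vaccine-versus-placebo estimate or interval for shedding if the four-arm test is not significant. That follows from the text alone and needs no power assumption.

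A reader might infer that the plan throws away about 15 points of power. The documents do not support that as a general statement. They give no subset size, shedding rate or effect, and the figure requires equal effects at all doses together with mid-range power. At the assumed 58 per arm and 50% placebo shedding, the pooled contrast ranges from a gain of about 15 points to a loss of 47, depending on the dose pattern. The case for adding it is that it answers the stated question and yields an interval, not that it is always the more powerful test. On an exploratory endpoint this is a worthwhile, low-cost improvement and no threat to the trial's primary conclusions.

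**What to change.** In Section 7.1.5, before unblinding, add two analyses of any-day shedding:

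- (a) All P2-VP8 doses against placebo, as a contrast from the logistic model already planned, with the risk difference and 95% CI, reported whatever the overall test shows.
- (b) A test for trend over the four ordered arms, with the scores stated.

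If a single p-value is wanted, combine (a) and (b) through a joint (max-contrast) critical value, which allows for the correlation between them. Keep the 3-df test and each dose versus placebo alongside. State the size of the stool subset so that the precision can be judged.

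The cost is one or two further contrasts from a model that will be fitted anyway, and one or two extra exploratory tests to interpret. The pooled contrast will have little sensitivity if only one dose works, which is why the dose-specific results must stay.
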